11.5.8.3. Six Month Visit

- Review medications
- Adverse event assessment
- Review symptoms suggestive of recurrent AF/AT/AFL
- Health care utilization assessment- collect information about hospitalizations or emergency department visits experienced by the subject since the last visit
- 12 lead ECG
- 24h continuous ECG monitoring with ambulatory monitoring equipment
- EQ-5D and AFEQT Questionnaires
- Review the patient-activated ambulatory monitoring instructions with the subject.
- Chest X-ray, including inspiration and expiration films, is required for subjects whose PNI was unresolved at the 3 month visit
- In the case of suspected PV stenosis, Magnetic Resonance Imaging (MRI) or Computerized Tomography Scanning (CT scan) is required. It is not required at this visit if it was already completed at an earlier visit and PV stenosis was confirmed.

11.5.8.4. Twelve month Office Visit

- Review medications
- Adverse event assessment
- Review symptoms suggestive of recurrent AF/AT/AFL
- Health care utilization assessment- collect information about hospitalizations or emergency department visits experienced by the subject since the last visit
- 12 lead ECG
- 24h continuous ECG monitoring with ambulatory monitoring equipment. The subject will be instructed to apply the continuous monitoring patches and complete the 24 hours of continuous monitoring within 7 days prior to the 12 month visit. It is recommended that the study personnel call the subject to remind them of this requirement. If the subject is not able to apply the device prior to the visit, it may be applied by study personnel at the 12 month visit.
- EQ-5D and AFEQT Questionnaires
- Collect the ambulatory monitoring equipment and return to Medtronic (or designee). If the subject did not perform the continuous monitoring prior to the 12 month visit, apply the device to the subject to complete 24 hour continuous monitoring. Give the subject instructions on how to return the equipment.
- Chest X-ray, including inspiration and expiration films, is required for subjects whose PNI was unresolved at the 6 month visit
- In the case of suspected PV stenosis, Magnetic Resonance Imaging (MRI) or Computerized Tomography Scanning (CT scan) is required. It is not required at this visit if it was already completed at an earlier visit and PV stenosis was confirmed.
- Inform the subject they have completed the study

11.5.9. Unscheduled Office Visits

An unscheduled visit is defined as any unplanned cardiovascular-related office visit at the study site that is performed by personnel participating in the study and occurs between CIP required visits. Submit to the core lab any 12 lead ECG or continuous monitoring completed in conjunction with an unscheduled office visit. The following information is required to be collected at unscheduled follow-up visits:

- Review medications
- Adverse event assessment
- Review symptoms suggestive of recurrent AF/AT/AFL
- Health care utilization assessment- collect information about hospitalizations or emergency department visits experienced by the subject since the last visit
- 12 lead ECG

11.5.10. Re-Ablation/Crossover Ablation

- Obtain approval from Medtronic for crossover ablations (not required for treatment arm reablation)
- Perform the following assessments prior to the cryoablation:
 - Review medications
 - Adverse event assessment
 - Review symptoms suggestive of recurrent AF/AT/AFL
 - EQ-5D and AFEQT Questionnaires
 - Health care utilization assessment- collect information about hospitalizations or emergency department visits experienced by the subject since the last visit
- Procedure Data:
 - Catheters used (i.e. Arctic Front Advance™, Freezor® MAX and Achieve™ Mapping Catheter, etc.)
 - Minimum temperature for each cryoapplication
 - Duration of each cryoapplication
 - Vein location for each cryoapplication (e.g. right superior PV)
 - Use of phrenic nerve pacing or other phrenic nerve monitoring technique for each cryoapplication, specifically those cryoapplications surrounding the RS and RI PVs
 - Demonstrated electrical block and, if real-time signals are available, time to isolation
 - Adjunctive catheters, mapping or visualization devices, sedation type, procedure information, esophageal temperature, ACT, cardioversion use and fluoroscopy time will be collected
 - Pulmonary vein isolation stats from previous ablation (re-ablations only)

11.5.11. 12 lead Electrocardiograms

All study required 12 lead ECGs will be sent to the core lab. The core lab will be responsible for adjudication of atrial arrhythmias for the primary objective of the study. The core lab will send the results of all ECG analyses to the Investigators for appropriate follow-up, if necessary, and assessment for adverse event reporting. Copies of additional source documents may be requested.

11.5.12. Ambulatory Monitoring

Market- released ambulatory monitoring equipment will be distributed by a core lab to centers after activation has occurred. Subjects will be provided with a small patient-activated electronic ambulatory

monitoring device after the AAD optimization (control arm) or post-ablation blanking period (treatment arm) ends. This device will serve two functions:

- 24 hour continuous monitoring: This is traditionally done using a Holter monitor. The investigative site personnel will apply the device patches for the subject during the subject's 6 month visit and train the subject how to apply the device. The subject will be asked to apply the continuous monitoring patches themselves prior to the 12 month study visit. Additionally, subjects may be asked to perform 24 hour continuous monitoring on their own if they miss a scheduled study visit.
- Patient-activated mode: Subjects will be asked to transmit ECG data weekly and whenever they experience AF symptoms. This mode does not require adhesive patches; the subject simply holds the device to his or her chest for a short period of time.

In both modes, the data automatically transmits to the core lab via a secured cell phone connection.

The core lab will manage maintenance, calibration and tracking of the ambulatory monitoring equipment. The core lab will be responsible for adjudication of rhythm documentation for the primary efficacy objective of the study. The core lab will send the results of all ambulatory monitoring analyses to the Investigators for appropriate follow-up, if necessary, and assessment for adverse event reporting.

Subjects will return the ambulatory monitoring equipment at the 12 month follow-up visit.

11.5.13. Study Exit

Subjects will be exited from the study upon completion of the 12 month follow-up visit. For information about subject withdrawal and discontinuation, see section 11.10.

11.6. Assessment of Efficacy

The primary efficacy objective is based on the data collected as discussed in section 5.1.1 and 5.1.4.

11.7. Assessment of Safety

The secondary safety objective is based on the Adverse Event data collected. Further information on the collection and assessment of safety data is discussed in section 13.

11.8. Recording Data

The study will collect data using an electronic data management system for clinical studies. Centers will enter data onto eCRFs within the database. The core lab will also enter data onto CRFs within a separate electronic database.

Procedures in the CIP require source documentation. Source documentation will be maintained at the study center. Source documents, which may include worksheets, subject medical records, and console files, must be created and maintained by the investigational center team. The data reported on the eCRFs shall be derived from source documents and be consistent with these source documents, and any discrepancies shall be explained in writing. The eCRF may be considered source for the following data collection elements:

- Time of isolation of the cryoablation catheter
- Esophageal temperature
- Investigator assessment of adverse event or death relatedness and severity

- Date center became aware of the adverse event, device deficiency or death
- Reason for study deviation
- Database generated patient reference ID

When copies or print-outs of the source documents are made, center personnel must sign and date any copies or printouts of original source documents with a statement that this is complete and true reproduction of the original source document. The sponsor or a regulatory authority may audit or inspect the study center to evaluate the conduct of the study.

The clinical Investigator(s)/institution(s) shall allow study related monitoring, audits, IRB/EC review and regulatory inspection by providing direct access to source data/documents. Further detail on data management is provided in Section 17.3.

11.9. Deviation Handling

A study deviation is defined as an event within the study that did not occur according to requirements specific to the CIP or CTA. Every attempt must be made to avoid study deviations. Prior approval by Medtronic is expected in situations where the Investigator anticipates, contemplates, or makes a conscious decision to deviate. In countries following ISO 14155:2011, prior approval for study deviations will be reported to local authorities and ethics boards per local requirements. If the deviation affects subject's rights, safety and well-being, or the scientific integrity of the study, prior approval from ethics board and/or competent authority (CA) is also required, depending on local legislations. Prior approval is not required when a deviation is necessary to protect the safety, rights, or well-being of a subject in an emergency or in unforeseen situations beyond the Investigator's control (e.g. subject failure to attend scheduled follow-up visits, inadvertent loss of data due to computer malfunction, inability to perform required procedures due to subject illness). Subjects' failure to submit ambulatory monitoring transmissions per the CIP do not require a deviation to be reported. Ambulatory monitoring transmission compliance will be tracked by Medtronic personnel and the Core Lab.

For medically justifiable conditions which preempt a subject's ability to complete a study required procedure, it may be permitted to report only one deviation which will apply to all visits going forward. This may also apply for other unforeseen situations (e.g. the subject permanently refuses to complete a study required procedure and the data will not contribute to the primary endpoint analysis.). However, prior approval from Medtronic is required for such situations.

All study deviations must be reported to Medtronic regardless of whether they are medically justifiable, pre-approved by Medtronic, an inadvertent occurrence, or taken to protect the subject in an emergency. The description of the deviation and justification must be documented and submitted to Medtronic via eCRF completion.

In the event the deviation involves a failure to obtain a signed Informed Consent Form, or is made to protect the life or physical well-being of a subject in an emergency, the deviation must be reported to the IRB/EC as well as Medtronic within five (5) working days. Reporting of all other study deviations should comply with IRB/EC policies and/or local laws and must be reported to Medtronic as soon as possible upon the site becoming aware of the deviation. Refer to

Table 9 for reporting requirements.

Medtronic is responsible for reviewing deviations, assessing their significance, and identifying any necessary corrective and/or preventive actions (e.g. amend the CIP, conduct additional training, and terminate the investigation). Repetitive or serious Investigator compliance issues may result in initiation

of a corrective action plan with the Investigator and center, and in some cases, may necessitate suspending a center's ability to enroll until the problem is resolved, or ultimately terminating the Investigator's participation in the study. Medtronic will provide center-specific reports to Investigators summarizing information on deviations that occurred at the investigational center on a periodic basis.

11.10. Subject Withdrawal or Discontinuation

A subject can withdraw from the study at any time. If the subject wishes to exit from the study (i.e. the subject revokes consent), the center is required to document the reason for exit on an eCRF. In addition, centers shall follow the regulations set forth by their IRB/EC.

Prior to exiting a subject from the study, it is recommended to follow the subject until all ongoing device and/or procedure related adverse events are resolved or unresolved with no further actions planned. An unscheduled office visit should be attempted if the subject exits the study outside of a scheduled follow-up visit.

Following exit, subjects will continue to receive standard medical care. Upon exiting from the study, no further study data will be collected or study visits will occur for the subject. All data available through the time of the subject's exit will be used for analysis.

Reasons for subject withdrawal or discontinuation include:

- Subject is lost to follow-up
- Subject did not meet inclusion/exclusion criteria after the date the subject signed the Informed Consent Form and prior to randomization.
- The subject was randomized to the treatment arm, but no cryoballoon ablation procedure was attempted
- The subject was randomized to the control arm, but no AAD was initiated
- Subject chooses to withdraw (e.g., Informed Consent Form withdrawal, relocation to another geographic location)
- Investigator deems withdrawal necessary (e.g., medically justified, inclusion/exclusion criteria not met, failure of subject to maintain adequate study compliance)
- The sponsor or regulatory authority decides the study will be closed or a particular center will be closed

The following information is required to be collected at early study exit:

- Reason for exit must be documented on the eCRF and in the subject's medical record
- An unscheduled office visit should be attempted if the subject exits the study outside of a scheduled follow-up visit

In the case that the subject is determined to be lost to follow-up, details of a minimum of two attempts and the method of attempt (e.g., one letter and one phone record or two letters) to contact the subject must be recorded. In addition, follow the regulations set forth by the governing IRB/EC.

12. Risks and Benefits

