5.1.4. Primary Endpoint

5.1.4.1. Primary Efficacy Endpoint

The primary endpoint is treatment success at 12 months after AAD initiation (control arm) or after the pulmonary vein isolation ablation procedure utilizing the Arctic Front Advance™ Cardiac CryoAblation Catheter (treatment arm). A treatment success is the opposite of a treatment failure.

Treatment failure is defined as any of the following components:

- a) Acute procedural failure (treatment arm only)
- b) Documented AF/AT/AFL on ambulatory monitoring/12-lead ECG after the 90 day post-ablation blanking period (treatment arm)/AAD optimization period (control arm).
 - o Minimum of 30 seconds on ambulatory monitoring or 10 seconds on 12-lead ECG.
 - o Note: Documented occurrence and treatment of typical right-sided cavotricuspid isthmus dependent atrial flutter is not considered a failure if confirmed by entrainment maneuvers during EP testing.
- c) Any subsequent AF surgery or ablation in the left atrium.
- d) Any subsequent cardioversion after the 90 day post-ablation blanking period (treatment arm)/AAD optimization period (control arm).
- e) Class I or III antiarrhythmic drug (or sotalol) use after the 90 day blanking period (treatment arm only).

The AAD optimization period is defined as the first 90 days after AAD initiation (control arm). The post-ablation blanking period is defined as the first 90 days after the index ablation procedure (treatment arm). Recurrences of atrial arrhythmias during the AAD optimization/blanking periods will not be counted in the determination of the first clinical failure for the primary endpoint.

Within the AAD optimization period/post-ablation blanking period, recurrent arrhythmias can be managed with medications or cardioversions. Reablation will be considered a primary endpoint failure at all times, including during the 90 day post-ablation blanking period.

Acute procedural failure (treatment arm only) is defined as:

- a) Inability to isolate all accessible targeted pulmonary veins (assessed for entrance block and, where assessable, exit block) during the index ablation procedure.
- b) Left atrial non-PVI ablations including but not limited to, ablation of linear lesions
- c) Use of a non-study device in the left atrium.

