11.4. Randomization and Treatment Assignment

Enrolled subjects are eligible for randomization after all inclusion and none of the exclusion criteria are met and after the baseline QoL questionnaires are completed. Subjects will be randomized in a 1:1 fashion to undergo a cryoablation procedure (treatment arm) or receive AAD therapy (control arm).

See Section 11.5.2 for control arm procedures and Section 11.5.3 for treatment arm procedures.

Subjects will be randomized using an electronic randomization system. The randomization schedule will be stratified by study site to ensure that within each study site randomization is approximately 1:1.

Subjects will be analyzed according to a modified intention-to-treat protocol: subjects who withdraw their informed consent prior to the index cryoablation procedure or initiation of AAD therapy will be excluded from the analysis of the primary safety and efficacy endpoints. Otherwise, the standard intention-to-treat protocol is applied: subjects who receive either therapy, regardless of what it actually is, will be analyzed according to their randomization status. This allows for the protection of the benefits of randomization, while avoiding the problem of attrition and adverse events occurring in the time between randomization and the initiation of treatment, which, due to the practicality of scheduling can be up to 30 days. All randomized subjects should be encouraged to comply with the study procedures until study closure.

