#### 6.1.3. Analysis Sets

The **Full analysis set** consists of all enrolled subjects who consent and meet the inclusion/exclusion criteria. [REDACTED]

The **Modified Intention-to-Treat (mITT)** cohort is the subset of subjects who maintain informed consent at least until the initiation of a cryoablation procedure or commencement of AAD treatment. For endpoints analyzed in this group of subjects, the standard intention-to-treat protocol applies immediately upon first receipt of a treatment (regardless of whether the assigned treatment was actually received). The mITT cohort will be used in the analysis of the primary efficacy objective, the secondary objectives regarding HCU and cardioversion, [REDACTED].

The **Cryo-Treated as Randomized (CTR)** set refers to eligible and consenting subjects who were randomized to cryoablation therapy and had a cryoablation procedure. The procedure is considered as

having been performed if a cryoballoon catheter was inserted into a subject's vasculature. This analytical cohort does not include AAD arm subjects who cross over into the cryoablation group, and does not include subjects who withdraw consent or are withdrawn by an investigator prior to their first day at risk for events. This set will be used in the analysis of the primary safety objective, [REDACTED].

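### CIP 11.10 allows exit of subjects who started the other arm's therapy, although the CIP and SAP keep those subjects in the primary analysis as randomised

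*Protocol*

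**What the plan says.** CIP 11.10 opens a list with "Reasons for subject withdrawal or discontinuation include". Two items mirror each other: "The subject was randomized to the treatment arm, but no cryoballoon ablation procedure was attempted" and "The subject was randomized to the control arm, but no AAD was initiated". Neither says what happens if the subject has started the other arm's therapy. The same section states "Upon exiting from the study, no further study data will be collected or study visits will occur for the subject", and also "All data available through the time of the subject's exit will be used for analysis".

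The analysis sections point the other way:

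- CIP 11.4: "subjects who receive either therapy, regardless of what it actually is, will be analyzed according to their randomization status". CIP 15 and 15.1.7 repeat the rule for anyone who starts either therapy.
- SAP 6.1.3 applies intention-to-treat within the mITT cohort from first receipt of a treatment, "regardless of whether the assigned treatment was actually received".
- CIP 6.1 promises follow-up of all randomised subjects to 12 months. CIP 11.4 asks that they be encouraged to comply until study closure.

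CIP 5.1.4.1 lists as a failure component "Class I or III antiarrhythmic drug (or sotalol) use after the 90 day blanking period (treatment arm only"). CIP 15.1.5 and SAP 6.2.2.4 set day 0 at the index cryoablation or the start of AAD. They censor subjects without failure at the last recorded contact, which may be the exit date.

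**The concern.** One subject can meet both rules. A cryo-randomised subject who starts an AAD instead of having the procedure has initiated a therapy, belongs to the mITT set and has a day 0. The same subject fits a listed reason for exit. If a site uses that reason before day 90, follow-up ends before AAD use can count as a failure, and the subject enters the Kaplan-Meier analysis as an event-free censored observation. The censoring is then tied to the outcome, which the Kaplan-Meier estimate and the log-rank test assume it is not.

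The control arm has the mirror case: a subject ablated without ever starting an AAD. In an unblinded comparison of a drug with a procedure, the two kinds of switch need not be equally common. The healthcare-utilisation and cardioversion analyses also use the mITT set and would lose the same follow-up.

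**Working it through.** **1. The rules applied to the two kinds of switcher**

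| | Cryo-randomised, starts AAD only | AAD-randomised, ablated only |
|---|---|---|
| In mITT as randomised (CIP 11.4, 15.1.7; SAP 6.1.3) | Yes | Yes |
| Fits an exit reason in CIP 11.10 | Yes | Yes |
| Outcome if followed | Failure if AAD use continues past day 90 | Unclear: the documents do not say whether a first ablation with no prior AAD counts as a subsequent left atrial ablation |
| Outcome if exited before day 90 | Censored event-free | Censored event-free |

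Day 0 can be read as the start of whichever therapy came first. The 90-day period, however, is tied to the assigned therapy (index ablation for the treatment arm, AAD initiation for the control arm). SAP 6.1.1 has disposition lines for withdrawal before therapy and for therapy started as randomised, but none for subjects who started the other therapy.

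**2. The plan's own figure**

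Inputs from SAP 7.1: 69.9% against 45.9% success, two-sided alpha 0.05, 90% power, 1:1.

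n per arm = [1.960 × √(2 × 0.579 × 0.421) + 1.282 × √(0.699 × 0.301 + 0.459 × 0.541)]² / 0.240² = 86.8, so 87 per arm and 174 in total. Power at 87 per arm is 0.901, and 174 / 0.90 gives 194 randomised. All agree with the plan. The 45% printed in CIP 15.1.6 would give 81 per arm, so the stated size comes from 45.9%.

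**3. Cryo-arm switchers**

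Assumptions: 105 per arm (210 randomised 1:1), 69.9% success in treated cryo subjects, 45.9% in the AAD arm, and every cryo switcher a failure if followed. The number of switchers k is not in the documents.

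If the k subjects exit early, the cryo estimate stays near 69.9% and the difference near 24.0 points. If they are followed and counted, cryo success = 69.9% × (1 − k/105). Power uses the same normal approximation as step 2.

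| k | Cryo success | Overstatement if exited (points) | Difference from 45.9% (points) | Power |
|---|---|---|---|---|
| 1 | 69.2% | 0.67 | 23.3 | 0.934 |
| 2 | 68.6% | 1.33 | 22.7 | 0.919 |
| 3 | 67.9% | 2.00 | 22.0 | 0.902 |
| 5 | 66.6% | 3.33 | 20.7 | 0.861 |
| 10 | 63.2% | 6.66 | 17.3 | 0.717 |

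With outcomes at their expected values, significance is lost at 16 of 105 switchers (15.2%, z = 1.94). With 95 analysed per arm it is lost at 14, and with 87 at 12.

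**4. Adding the control arm (5 switchers in each arm named)**

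- Control switchers only, all failures: AAD success = 45.9% × 100/105 = 43.7%; difference 69.9 − 43.7 = 26.2 points.
- Both arms, all failures: 66.6 − 43.7 = 22.9 points.
- Cryo switchers fail, control switchers succeed at the cryo rate: AAD success = (45.9 × 100 + 69.9 × 5)/105 = 47.0%; difference 19.5 points.

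Against 24.0 points with all of them exited, the as-randomised difference can be larger or smaller.

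**The case against.** The strongest reply is that CIP 11.10 records reasons for exit and orders nothing. Its list is introduced as reasons that may be included, whereas the CIP does order exit elsewhere: CIP 11.5.1 requires it when a cardiac thrombus is seen before ablation. CIP 6.1 and 11.4 point towards continued follow-up. The two items fit naturally with subjects who start no therapy at all, which is how SAP 6.1.1 describes withdrawals before therapy. Early switching is not a planned path either. CIP 11.5.2 allows crossover to ablation only after treatment failure and with sponsor approval, CIP 11.5.3 calls for the procedure within 30 days, and deviations must be reported.

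This stands as far as it goes. A reader might infer that the plan removes switchers and that the as-randomised analysis cannot be done. The text supports less: exit is allowed, and the analysis fails only for switchers who are actually exited. Nor do such subjects vanish or get analysed as treated. They stay in their randomised arm, with data up to exit, and are censored.

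SAP 6.4.1 also offers a safeguard. Its tipping-point analysis turns censored cryo subjects into failures and censored AAD subjects into successes, one at a time, until the conclusion changes. With fewer than 5 subjects missing, a worst-case analysis replaces it. That probes this kind of loss, but as a sensitivity analysis on the full analysis set. It does not correct the primary estimate or test, and it assumes outcomes that continued follow-up would observe.

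The narrow reading of the two items may well be what was meant. The section does not say so, and a site could follow its wording and exit a subject whom the analysis sections need.

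**Conclusion.** The conflict is real and should be removed. CIP 11.10 allows exit, with no further data, of subjects whom CIP 6.1, 11.4, 15 and 15.1.7 and SAP 6.1.3 keep in the analysis as randomised. For a cryo-randomised subject who stays on a Class I or III AAD, exit before day 90 replaces a failure with a censored observation.

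The size rests on assumptions. The documents give neither a switching rate nor the timing of exits. If every such cryo subject would have failed, each one exited adds about 0.67 points to cryo success at 105 per arm, or 1.3 to 3.3 points for 2 to 5 subjects. By itself this is unlikely to reverse the conclusion: at the planned rates, 12 to 16 cryo switchers would be needed, depending on whether 87 or 105 per arm are analysed.

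A reader might also infer that the bias favours cryoablation. For the cryo-arm item alone it does. Because the control-arm item mirrors it, the net direction depends on unknown counts and on how a control subject's first ablation is scored. No stated sample size or power figure is wrong on this account.

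**What to change.** - **CIP 11.10:** limit the two exit reasons to subjects who start neither therapy. State that a subject who starts the other arm's therapy stays on the 12-month schedule unless consent is withdrawn. Reconcile the thrombus exit in CIP 11.5.1 with the same follow-up promise.
- **SAP 6.2.2.4:** for these subjects, state that day 0 and the 90-day period run from the first therapy started, and that the failure components of the randomised arm apply. State whether a control subject's first ablation, with no AAD before it, counts as a subsequent left atrial ablation.
- **SAP 6.1.1:** add a line to the disposition figure for subjects who started the other arm's therapy, by randomised arm.

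The cost is a few sentences in each document and scheduled follow-up of a small number of subjects already among the 210. The sample size does not change.
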